15.5 Concise Health Risk Tracking - Self Report (CHRT-SR) Suicidal Behavior Evaluation

The CHRT-SR [161] is a 16-item participant self-report assessment of suicidality and related thoughts and behaviors. The scale is designed to quickly and easily track suicidality in a manner consistent with the Columbia Classification Algorithm of Suicide Assessment (C-CASA) [162]. The CHRT-SR will be assessed at screening, treatment initiation, the safety visit, and weeks 4, 8, 12, 16, 20, and 24 (or the end of study visit, if not week 24). The CHRT-SR will assess high risk suicidal ideation by a positive response (Agree or Strongly Agree) on any of the last three questions (thoughts of, thoughts of how and/or a specific plan to commit suicide) and prompt a clinician assessment for suicide risk before leaving the clinic.

15.6 Concise Health Risk Tracking - Clinician Rated

The Clinician Rated (CHRT-CR) [161] assessment will be performed by the study clinician only if a participant answers any of questions 14-16 on the CHRT-SR as “Agree” or “Strongly Agree” as described in Section 15.5.

15.7 Patient Health Questionnaire (PHQ-9) Depression Symptoms

We measure depression symptoms using the self-reported PHQ-9, a 9-item scale validated for screening, diagnosing, and assessing the severity of depression symptoms in diverse populations [163]. The PHQ-9 will be administered at baseline, 12, and 24 weeks (or the end of study visit, if not week 24). Endorsements of suicidality on the PHQ-9 will be addressed locally at each site.

15.8 Suicidal Risk

This assessment will be performed by research staff if the participant endorses suicidality on the PHQ-9 by answering Q9 (“Thoughts that you would be better off dead, or of hurting yourself in some way”) as “Several days”, “More than half the days” or “Nearly every day.”

16.0 STUDY CONDITIONS

The two study conditions are: 1) office-based XR-NTX, and 2) TAU. Study conditions are discussed in detail in section 4.2, 4.3, and 9.0.

16.1 Clinic-Based XR-NTX

The office-based XR-NTX study condition is discussed in detail in Sections 4.2 and 9.0.

16.2 TAU

The TAU study condition is discussed in detail in Sections 4.3 and 9.0.

16.3 Training

Training in study-specific assessments will be provided as specified in a comprehensive training plan that will be developed by the Lead Team, which includes the Lead Node, CCTN, CCC and DSC staff. The training sessions will include modules targeting all research team members conducted via web, telephone and/or in-person training sessions. Training will cover standard NIDA training for all CTN Trials (e.g., Human Subjects Protection and Good Clinical Practices), as well as protocol specific training as needed (e.g., assessments, study intervention, fidelity to the protocol, safety procedures, data management and collection, research procedures). Attention will be given to provide the study clinic staff providers training in management of opioid and alcohol withdrawal, XR-NTX induction and maintenance, and to familiarize study personnel with study procedures. Support mechanisms are identified (e.g., who to contact for aid, questions, resources) as well as re-training procedures. All study staff will be required to complete any local training requirements per study site and IRBs. Further details are presented in the study Training Plan.

16.4 Concomitant Medications

Participants will be instructed to contact the study clinician at their research site if they plan on taking any concomitant medications (including prescription, over-the-counter, and herbal supplements) during the course of the study. Concomitant medications will also be assessed at screening.

As described in the eligibility criteria, participants will be excluded if there is a need for ongoing opioid analgesic treatment. The study clinician may also exclude any participant taking medications that could interact adversely with study drugs, at his/her clinical discretion.

Study screening and treatment induction procedures (requirement for negative UDS for opioids on day of induction – XR-NTX arm only) are anticipated to greatly decrease the risk of precipitating opioid withdrawal. In the event a participant experiences opioid withdrawal following XR-NTX injection, the study clinician may dispense symptomatic treatments (e.g., oral clonidine, prochlorperazine, ibuprofen, etc.) to alleviate symptoms of opioid withdrawal, according to local SOPs. XR-NTX can also be associated with transient nausea unrelated to opioid withdrawal, typically lasting 2-8 hours. Should participants develop nausea or vomiting during naltrexone induction, this will be treated with oral anti-emetics (e.g., prochlorperazine) as needed.

17.0 STATISTICAL ANALYSIS

17.1 Primary Objective of the Analysis

The Primary objective of the CTN-0067 CHOICES scale-up study is to discover whether HIV clinic-based XR-NTX is non-inferior to TAU with respect to HIV viral suppression in HIV-infected participants with opioid use disorder. We have chosen a non-inferiority margin of 0.75. That is, we will reject the null hypothesis of inferiority of XR-NTX to TAU in favor of non-inferiority if the lower 95% confidence limit for the ratio $\frac{\text{Pr}(\text{suppressed}|\text{NTX})}{\text{Pr}(\text{suppressed}|\text{TAU})}$ is strictly greater than 0.75. We anticipate a sample size of 350 (175/arm) will grant at least 80% power for the non-inferiority conclusion.

17.2 Primary Outcome Measure

The primary outcome measure for CTN-0067 CHOICES scale-up study is HIV viral suppression. HIV viral suppression is defined as an HIV-1 RNA ≤ 200 copies/ml at 24 weeks from time of randomization.

The binary RMVL model of Rose et al. will be used to predict the log of the risk ratio (not the log of the odds) for suppression via a generalized estimating equation with an exchangeable covariance structure for all the values of a single participant. Baseline alcohol use disorder and sites are included as fixed effects. The fixed effects part of the model is thus:

$$\log(p_{ij}) = \alpha + \beta * \text{trt}_i + \gamma * \text{month}_j + \theta * \text{trt}_i * \text{month}_j + \tau * \text{alc}_i + \delta_1 * \text{site}_{1i} + \dots + \delta_k * \text{site}_{ki}$$

where p_{ij} is the probability of suppression of participant i in month j , trt is the indicator for treatment, months enter linearly, there is a time by treatment interaction, alc is an indicator for baseline alcohol use disorder, and $\text{site}_1, \dots, \text{site}_k$ are site indicator variables. The model will incorporate 2 time points for each patient (months 3 and 6), with a contrast used to estimate the treatment effect at month 6. The following SAS fragment shows how to implement this analysis:

```
proc genmod data = visits descending;
  class suppressed trt site projid alc base;
  model suppressed = trt | month alc site / dist = bin link = log;
  repeated subject = projid / type = exch;
  estimate "6M trt eff" trt 1 -1 trt * month 6 -6
  run;
```

Note that the estimate statements assumes the following coding: $\text{trt} = (\text{ntx}, \text{tau})$ $\text{month} = (3, 6)$.

The RMVL is a type of longitudinal model. In theory, longitudinal models can accommodate missing data better than non-longitudinal models because they incorporate all non-missing data points. But this approach assumes that missing data are not informative, that is, that missing values are probably similar to corresponding non-missing values with the same set of other predictors. For trials of substance-using individuals, missing at random (MAR) is less likely than missing not at random (MNAR) alternative: if data are missing, it is probably because the participant is unsuppressed. So, for the primary analysis, “unsuppressed” will be substituted for missing suppression status values. An exception is that, if missing data are flanked on both sides by “suppressed” values, we will impute the missing data to be suppressed. Since death is at least

as undesirable as lack of suppression, “unsuppressed” will be assigned as a status value for visits subsequent to death. A secondary sensitivity analysis will explore the extent to which trial conclusions need to be changed as the missingness assumption approaches MAR.

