6.3 Justification of 24 weeks active treatment and timing of ART initiation

Assessment of the primary outcome of HIV viral suppression requires a minimum of 6 months, given the high potency of currently available ART regimens. While longer follow-up periods are required to assess sustained viral suppression, nearly all people initiating ART can now achieve an HIV viral RNA \leq 200 copies/mL within 6 months of ART initiation. Participants not already taking ART at study enrollment will be encouraged to begin ART as soon as possible following enrollment. The timing of XR-NTX initiation or ART initiation is up to the discretion of the HIV provider on the basis of the patient's clinical priorities. Finally, previous efficacy trials of XR-NTX for opioid use disorder [55] and alcohol use disorder [64] provided 24 weeks of XR-NTX.

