9.1.9 Randomization

The timing of randomization will follow shortly after baseline assessments and final confirmation of eligibility. Participants will be encouraged to initiate treatment within 28 days of randomization. If a participant is unable to initiate treatment within 28 days, he or she may initiate XR-NTX study drug at any time until week 20 and may initiate TAU at any time during the trial. Initiation of assigned treatment will be tracked.

Participants will be randomized in a 1:1 fashion to either office-based XR-NTX or TAU using a permuted block design with randomly-sized blocks. Randomization will be stratified only by site. Participants who meet DSM-5 criteria for both opioid and alcohol use disorder (16% of CTN-0055 CHOICES pilot study participants) will be included, in addition to participants with OUD, alone.

Concomitant alcohol use disorder will be considered as a potential covariate [31], [127, 128]. Participants need not be abstinent from opioids at the time of randomization.

The randomization procedure will be conducted in a centralized process through the Data and Statistics Center (DSC). Specifically, randomization schedules will be created by the study statistician for each site. The randomization schedules will be of a randomized-block nature to ensure relative equality of assignment across condition across the recruitment period and to prevent the potential for study staff guessing the next assignment, which is heightened when a fixed block-size is used. After the baseline assessment is successfully completed, a designated site study staff member will perform the randomization. Randomization for each participant is done over the internet using the Enrollment Module in Advantage eClinical.

The DSC statistician will review the randomization data on a regular basis to ensure that the scheme is being implemented according to plan. If a participant drops out of the study at any point after randomization, the randomization slot will not be re-allocated to a new participant due to the intent-to-treat nature of the study.

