11.0 HIV-RELATED MEASURES

11.1 Antiretroviral Medication Prescription and Adherence

Since HIV viral suppression is most strongly influenced by optimal use of ART, evaluation of adherence to one's ART regimen is essential. Self-reported antiretroviral use and adherence will be assessed using a Medication Adherence questionnaire with visual analogue scale [142, 143] that is administered at baseline, treatment initiation, and weeks 4, 8, 12, 16, 20 and 24 weeks or the end of study visit (if not week 24) for assessment of secondary outcome if participant is prescribed ART at the time of follow-up visits. The Medication Adherence questionnaire asks the participant about adherence to HIV medications in the past month. We will assess the proportion of participants taking 100% of prescribed ART doses, based on visual analogue scale responses, in the past month at baseline, treatment initiation, and weeks 4, 8, 12, 16, 20, and 24 for those prescribed ART (proportion; self-reported medication adherence measure).

Because self-reported use of specific antiretrovirals has limited reliability when compared with medical record review [144, 145], we will confirm ART use with medical record review at baseline and 24 weeks (or the end of study visit, if not week 24) using the ARV Medication Log to assess the secondary outcome of ART prescription. Specifically, we will assess change in the proportion of participants prescribed ART within 24 weeks following randomization, compared to baseline (binary; medical record abstraction).

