17.7 Rationale for Sample Size

Figure 4 shows the non-inferiority margin required for power of (0.8, 0.9) (using the lower tail of the two-sided 95% confidence interval) as a function of the sample size for the non-inferiority test of XR-NTX versus TAU at 4 months, as estimated from data “random-assignment-bootstrapped” from the (opioid + overlap) group who were unsuppressed at baseline in the pilot study (CTN-0055). There are only 9 participants in the bootstrap population: 7 in Core and 2 in UBC. The random-assignment bootstrap approach was used at 4 months as a conservative way to estimate power in the scale-up (see appendix). The margin is expressed in terms of the risk ratio (RR), that

is, $\Pr(\text{suppressed} \mid \text{XR-NTX}) / \Pr(\text{suppressed} \mid \text{TAU})^1$. A horizontal reference line in **Figure 4** marks $\text{RR} = 0.75$, and vertical reference lines mark the intersection of the horizontal line with the power curves for $(0.8, 0.9)$. The vertical lines intersect the N axis at sample sizes of about $(350, 480)$. For a given sample size, use of a margin at or below the one specified by the relevant curved line will grant power in excess of that depicted by the line. For example, an RR margin less than or equal to 0.75 will grant a power of at least 90% for total sample size (both arms together) of about 480 , and will grant a power of at least 80% for total sample size of 350 . We have chosen this last point upon which to base our sample size.

This particular example is calculated using the Rose et al. binary RMVL model. The fixed effects in the model are treatment, visit number (continuous), time by treatment interaction, baseline alcohol, and site (categorical). The data for each participant are assumed to have an exchangeable correlation structure. Missing data are assumed to be unsuppressed. Note that cases in which the model failed to converge or converged but SAS flagged the result as questionable have been dropped from this analysis. The number of analyzed iterations was $(9020, 9492, 9696, 9819, 9848, 9869, \text{ and } 9911)$ for $n = (200, 250, 300, 350, 400, 450, 500)$, respectively. With the assumptions above, a non-inferiority sample size calculation was performed using commercial software PASS and got very similar results.

17.7.1 Figure 4. Non-inferiority margins granting power = 0.8 and 0.9 as a function of sample size

Additional Comments Concerning Choice of RR margin

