17.11 Interim Monitoring of Primary Efficacy Endpoint

Interim monitoring will be performed of the primary alternative hypothesis that XR-NTX is non-inferior to TAU at 6 months of follow-up, using a non-inferiority risk ratio of $RR = \text{Pr}(\text{suppressed|NTX})/\text{Pr}(\text{suppressed|TAU}) = 0.75$. There will be no interim efficacy monitoring before 1/3 the participants have attained 24 weeks of follow-up and a sample size-re-estimation is performed (see the sample size re-estimation section below). Assuming the re-estimation does not call for a change in sample size (which would have to be ratified by the DSMB and approved by NIDA), we will on every subsequent DSMB meeting perform interim efficacy monitoring. All interim monitoring will use an O’Brien-Fleming-type boundary with information fraction equal to the proportion of the target sample size with primary outcome, and $\alpha = 0.025$, one-tailed.

Before recommending early termination, the DSMB will consider:

- Internal consistency of primary and secondary results.
- Internal consistency of primary and secondary results by subgroups defined by baseline characteristics.
- Distribution of baseline prognostic factors among the two groups.
- Consistency of primary and secondary results across sites and among sites enrolling larger numbers of participants.
- Possible bias in assessment of primary and secondary response variables.
- Possible impact of missing data from missed participant visits for assessment of the primary and secondary response variables.
- Possible differences in concomitant interventions or medications.

[figure not shown]
Sample Size Re-estimation

We plan to also perform a sample size re-estimation after about 1/3 off the total expected number of participants ($n=116$) attain their 24 week outcome, which is approximately 13 months into enrollment. The motivation for sample size re-estimation is that the original sample size calculation was based not only on a hypothesized treatment effect, but also on assumptions about nuisance parameters such as variances and attrition. In the case of CTN-0067, these nuisance parameter estimates are implicitly contained in the Random Assignment Bootstrapping approach we adopted for our sample size calculation, based on pilot data from CTN-0055. It seems reasonable to supplant that calculation with one based on ~100 actual CTN-0067 observations.

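### The primary model could also adjust for screening HIV RNA and baseline ART prescription, both already collected: a modest gain in precision at almost no cost, not an error

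*Combined protocol and SAP*

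**What the plan says.** **Primary model.** Section 17.2 models the log probability of suppression at months 3 and 6 with an exchangeable GEE. The terms are treatment, month, their interaction, alcohol use disorder and site: "Baseline alcohol use disorder and sites are included as fixed effects". The equation and the SAS MODEL statement agree with the text, and Section 17.7 lists the same terms for the power simulation. The CLASS statement, "class suppressed trt site projid alc base", names a variable `base` that is not defined and appears in no model term.

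**Allocation.** Section 9.1.9: "Randomization will be stratified only by site".

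**Baseline data in hand.** Section 7.1 requires a qualifying HIV RNA above 200 copies/ml for entry, and Section 13.5 schedules that assay at screening. For ART, Section 11.1 says "we will confirm ART use with medical record review at baseline and 24 weeks". The Section 10.1 table places the ARV Medication Log at the baseline visit, which precedes randomization.

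**Prognosis.** Section 11.1 opens with "Since HIV viral suppression is most strongly influenced by optimal use of ART". Section 6.3 says that "nearly all people initiating ART can now achieve an HIV viral RNA" at or below 200 copies/mL within 6 months.

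**Other analyses.** The covariate adjustment in Section 17.9.1 is for secondary outcomes and names neither variable. The sensitivity analyses in Sections 17.2 and 17.10 cover missing data, treatment received and per-protocol comparisons.

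**The concern.** The plan already adjusts for one patient-level factor, alcohol use disorder, but not for the two baseline variables closest to the outcome: the starting viral load, and whether ART had been prescribed before randomization. If they predict week-24 suppression, leaving them out makes the interval that is compared with 0.75 wider than it needs to be. The planned power rests on a bootstrap of nine pilot participants, so precision that requires no new data is worth having.

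A smaller matter concerns the qualifying HIV RNA. It may come from the chart and predate randomization by months, and no planned analysis looks at its age. Section 4.3 itself warns that participants suppressed at baseline push the result toward non-inferiority.

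**Working it through.** **1. The plan's own power.** Inputs: 175 per arm, margin 0.75, lower limit of the two-sided 95% interval, true RR = 1 (Sections 17.1 and 17.7, Appendix C). With common suppression rate p:

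power = Φ(−ln 0.75 / √[2(1−p)/(175p)] − 1.96)

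- p = 0.50: SE 0.107, power 76.8%
- p = 0.52: 80.0%
- p = 5/9 (pooled last pilot status, Section 17.7): 85.3%
- p = 0.573 (the BHIVES rate, Section 17.6): 87.6%

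The stated 350 for 80% corresponds to p of about 0.52. The exact figure comes from a bootstrap of individual pilot records, so a closed formula cannot reproduce it.

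**2. Predictor strength.** The documents do not give it. Assume that the two variables explain R² = 4% to 14% of the variation in week-24 suppression beyond alcohol use disorder and site. For a single yes/no predictor split 50:50 and p = 0.50, R² is the squared difference in suppression: √0.04 = 0.20 and √0.14 = 0.37, that is, 20 to 37 points.

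**3. Power after adjustment, by formula.** Multiply the variance by 1 − R²: Φ((z(power₀) + 1.96)/√(1−R²) − 1.96).

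| Unadjusted | R² = 4% | R² = 14% |
|---|---|---|
| 76.8% | 78.4% | 82.7% |
| 80.0% | 81.6% | 85.6% |
| 87.6% | 88.9% | 91.9% |

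**4. Simulation of the two-visit model.** 6,000 trials per cell, n = 350, 8 sites, assignment permuted within site, months 3 and 6, exchangeable GEE, log link, Poisson working variance, robust SE, month-6 contrast. Covariates: ART (50% prevalence) and standardized log10 RNA. Chance of declaring non-inferiority, unadjusted / adjusted:

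| p | R² | True RR 0.75 | True RR 1 |
|---|---|---|---|
| 0.50 | 0 | 2.8 / 2.9% | 76.9 / 76.6% |
| 0.50 | 4% | 2.5 / 2.8% | 76.8 / 77.9% |
| 0.50 | 14% | 2.5 / 2.8% | 76.6 / 81.5% |
| 0.573 | 0 | 2.9 / 2.9% | 87.0 / 86.8% |
| 0.573 | 4% | 2.7 / 2.7% | 87.3 / 88.2% |
| 0.573 | 14% | 2.7 / 2.6% | 86.8 / 91.1% |

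Gains are 0.9 to 4.9 points; the loss with useless covariates is 0.2 to 0.3 points. The Monte Carlo standard error of a 2.5% rate is √(0.025 × 0.975/6,000), about 0.2 points. No fit failed. A separate simulation (month 6 only, 4,000 trials per scenario, RR standardized from a logistic model) gave gains of about 1 point at R² near 3%, 2 to 3 points near 7% and 5 points near 14%.

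**5. Chance imbalance.** The difference between arms in the share q prescribed ART has SD √(2q(1−q)/175). A difference of 10 points or more occurs in 4.1% (q = 0.3), 6.1% (0.5) or 5.6% (0.6) of trials; the values of q are assumed. With an ART effect d, such an imbalance moves an unadjusted RR of 1.00 to (0.5 − 0.05d)/(0.5 + 0.05d): 0.96 for d = 0.20 and 0.93 for d = 0.37, or as far the other way. On the log scale that is 0.4 to 0.7 of the 0.107 standard error in step 1.

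**6. Age of the qualifying RNA.** Up to 90 days at consent (Section 7.1) plus up to 60 days to randomization (Section 9.1.3) gives 150 days. If a cut-off splits the trial in half (87.5 per arm), the step 1 formula gives power of 48% (p = 0.50) to 60% (p = 0.573) within a half.

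**The case against.** The strongest reply is that nothing is wrong. The test is valid as written, the claim of at least 80% power is met at the suppression rates the plan cites, and alcohol use disorder was a deliberate choice. That stands.

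The prognostic evidence is also thinner than it looks. Section 11.1 speaks of optimal ART use, not of prescription at baseline. Everyone enrolled is viraemic, so a participant already prescribed ART is viraemic despite it, while providers are encouraged to offer ART within 4 weeks to those without it (Section 9.2.1). Even the direction of the effect is uncertain. Counting missing results as unsuppressed may weaken virological predictors further. This stands as a reason to expect a modest gain; adjustment does not require the direction to be known.

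The simulation is not the plan's exact model. It uses a Poisson working variance, and alcohol use disorder is not among its covariates, so the assumed strength must be read as what the two variables add beyond it. At p = 0.50 and 4%, taking the type I shift from 2.5% to 2.8% at face value would account for about 1.5 points, more than the 1.1-point gain seen there. The cell at p = 0.573, with no such shift, still gains 0.9.

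A reader might also infer several stronger points that the documents do not support:

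- *Chance imbalance is left unhandled.* The confidence interval already reflects it, and Section 17.11 has the DSMB consider the balance of prognostic factors before recommending early termination.
- *The log-binomial model will fail in this trial.* Section 17.7 does report that "cases in which the model failed to converge or converged but SAS flagged the result as questionable have been dropped from this analysis", but those runs resampled nine people, and analysed runs rose from 9,020 at n = 200 to 9,819 at n = 350. This supports a fallback, not a replacement.
- *`base` shows that baseline adjustment was intended or is performed.* It enters no model term.
- *Section 9.1.7 contradicts the schedule by implying an HIV RNA at randomization.* Read in full, it places HIV-1 RNA at screening, in line with Sections 10.1 and 13.5.
- *Old qualifying results inflate type I error.* Participants already suppressed at entry would reduce assay sensitivity, not break the test in the enrolled population. The documents do not give their share, and age is only a proxy for suppression.

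**Conclusion.** The point holds as an improvement that is nearly free, not as an error. The primary model leaves out two plausibly prognostic variables that are collected before randomization, and the cost is precision only. Adding them would raise power by about 1 to 5 points if they explain 4–14% of outcome variation beyond alcohol use disorder and site, and would lose about 0.3 points if they explain nothing. That strength is assumed, so the true gain could be close to zero. Type I error is essentially unchanged. The documents do not support reading the omission as bias in the non-inferiority test. The age of the qualifying RNA is a supportive add-on; the case for adjustment does not depend on it.

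**What to change.** Before any comparison of outcomes by arm, and so before the interim looks in Section 17.11:

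- Add log10 screening HIV RNA and baseline ART prescription (yes/no) to the primary log-link GEE. Use pre-randomization values only, since ART prescribed after randomization is a secondary outcome. Keep the month-6 risk ratio and the 0.75 margin.
- Prespecify what replaces the log-binomial fit if it does not converge: a Poisson working variance with robust SE, or a standardized RR. Both keep the margin on the ratio scale.
- Recheck power under this model at the n = 116 re-estimation, which pools the arms and for which the plan already says "It seems reasonable to supplant that calculation with one based on ~100 actual CTN-0067 observations".
- As housekeeping, define `base` or delete it.
- Optionally, prespecify a sensitivity analysis of the primary RR by age of the qualifying HIV RNA at randomization. Report it with intervals and not as a second non-inferiority test, and state that any cut-off is an imperfect proxy for suppression. The draw date is already needed to apply the 90-day rule.

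No new data, visits or participants are needed. The change does alter the primary model, so the power in Section 17.7, simulated under the present covariates, must be checked again.
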